6.3.1.2. Hypertension

Hypertension is a known AE associated with Regorafenib treatment. Subject will have their blood pressure measured at least weekly at the study site during the first 6 weeks of treatment. If additional blood pressure measurements are done outside the study site, and the blood pressure is > 140 mm Hg systolic or > 90 mm Hg diastolic (NCI CTCAE v4.0), then the subject must contact study personnel. The management of hypertension, including the choice of antihypertensive medication, will be performed according to local standards and to the usual practice of the investigator. Every effort should be made to control blood pressure by medical means other than study drug dose modification. If necessary, Table 6-4 outlines suggested dose reductions.

**Table 6-4: Management of Treatment-Emergent Hypertension**

Grade (CTCAE v4.0)	Antihypertensive Therapy	Regorafenib Dosing
1 Prehypertension (systolic BP 120 - 139 mmHg or diastolic BP 80 - 89 mmHg)	None	
 Continue Regorafenib Consider increasing blood pressure (BP) monitoring
2 Systolic BP 140 - 159 mmHg or diastolic BP 90 - 99 mmHg, OR Symptomatic increase by > 20 mmHg (diastolic) if previously within normal limits	
 Treat with the aim to achieve diastolic BP ≤ 90 mm Hg: If BP previously within normal limits, start anti-hypertensive monotherapy If patient already on anti-hypertensive medication, titrate up the dose. 	
 Continue Regorafenib If symptomatic, hold Regorafenib until symptoms resolve AND diastolic BP ≤ 90 mm Hg^a. When Regorafenib is restarted, continue at the same dose level.
3 Systolic BP ≥ 160 mmHg or diastolic BP ≥ 100 mmHg OR More than one drug or more intensive therapy than previously used indicated	
Treat with the aim to achieve diastolic BP ≤ 90 mm Hg: Start anti-hypertensive medication
 
AND/OR Increase current anti-hypertensive medication
 
AND/OR Add additional anti-hypertensive medications.
	
 Hold Regorafenib until diastolic BP ≤ 90 mm Hg, and if symptomatic, until symptoms resolve.^a When Regorafenib is restarted, continue at the same dose level. If BP is not controlled with the addition of new or more intensive therapy, reduce by 1 dose level.^b If Grade 3 hypertension recurs despite dose reduction and antihypertensive therapy, reduce another dose level.^c
4 Life-threatening consequences (eg, malignant hypertension, transient or permanent neurologic deficit, hypertensive crisis)	Per institutional guidelines	Discontinue therapy

a. Patients requiring a delay of >4 weeks should go off protocol therapy

b. If BP remains controlled for at least one cycle, dose re-escalation permitted per investigator's discretion.

c. Patients requiring dose reductions below 80 mg daily should go off protocol therapy.

Liver Function Abnormalities

For patients with observed worsening of serum liver tests considered related to Regorafenib (i.e. where no alternative cause is evident, such as post-hepatic cholestasis or disease progression), the dose modification and monitoring advice in Table 6-5 should be followed.

Regorafenib is a UGT1A1 inhibitor. Mild, indirect (unconjugated) hyperbilirubinemia may occur in patients with Gilbert's syndrome.

Table 6.5: Dose Modification/interruption for alanine aminotransferase and/or aspartate aminotransferase increases related to study drug

Increases in ASL/ALT (per NCI-CTCAE v 4.0)	1st Occurrence	Restart	Recurrence
AST and/or ALT < 5 X ULN (<Grade 3)	Continue dosing, with weekly monitoring of liver function until transaminases return to < 3 X ULN (< Grade 1) or baseline.		
ALT and/or AST > 5 X ULN (> Grade 3)	Interrupt dosing, with weekly monitoring until transaminases return to < 3 X ULN or baseline.	If the potential benefit of reinitiating Regorafenib is considered to outweigh the risk of hepatotoxicity: reduce 1 dose level and measure serum transaminases weekly for at least 4 weeks.	Discontinue
ALT and/or AST > 20 X ULN (> Grade 4)	Discontinue		
ALT and/or AST > 3 X ULN (> Grade 2) with concurrent bilirubin > 2 X ULN	Discontinue treatment and measure serum transaminases weekly until resolution. Exception: subjects with Gilbert's syndrome who develop elevated transaminases should be managed as per the recommendations outlined above for ALT/AST elevations.		

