8.3 Statistical and analytical plans

The primary endpoint of the study is the rate of progression free survival (PFS) at 6 months (PFS6). Given the poor prognosis of this patient population and data from other studies of salvage therapy, a PFS6 of $\geq 20\%$ is felt to be important for this regimen, while a PFS6 $< 5\%$ is felt to be of poor interest. The trial also enrolls patients who progress within 6 months of last cycle of prior chemotherapy to enhance the interpretability of outcomes, since such patients are unlikely biologically to be progression-free for 6 more months without active therapy that favorably impacts on tumor biology to extend PFS. SAS version 9.3 was used to calculate power. The justification for the proposed sample size is based on an exact test for a binomial proportion with a one-sided significance level of 5%. With 32 evaluable subjects,

we will have approximately 80% power (79.6%) to reject the null hypothesis that PFS6 is < 5% in favor of PFS6 \geq 20%. Given that 5-10% of patients may be inevaluable, up to 35 patients may be enrolled. If five or more patients remain progression-free at 6 months, this regimen will be considered to be of significant interest.

Chi-square or Fisher's exact test will be employed to determine univariate association of biomarker status with PFS6 and objective response. Descriptive statistics including frequencies and proportions will be calculated to summarize safety and toxicity outcomes. Specifically, the number of adverse events (AE) and serious adverse events (SAE) will be tabulated and summarized. Point estimates and exact binomial (Clopper-Pearson) confidence intervals (CI) will be calculated to estimate the incidence of AEs and SAEs. The precision of these estimates, i.e., width of the confidence interval, will depend on the estimated incidence of each outcome. The table below gives the exact 95% confidence intervals for a range of incidences, assuming 32 evaluable subjects.

Number of subjects experiencing event	Estimated Incidence	95% Exact CI for Incidence		Width of CI
		Lower Limit	Upper Limit	
1	0.031	0.001	0.162	0.161
2	0.062	0.008	0.208	0.200
4	0.125	0.035	0.290	0.255
8	0.250	0.115	0.434	0.319
16	0.500	0.319	0.681	0.362

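### Table 6-4 gives opposite regorafenib instructions for an asymptomatic patient already on antihypertensives whose pressure is in the Grade 2 band: the Grade 2 step-up in treatment also meets the Grade 3 definition

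*Combined protocol and SAP*

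**What the plan says.** The Grade 2 row of Table 6-4 covers the patient who is already treated: "If patient already on anti-hypertensive medication, titrate up the dose". Its dosing column reads "Continue Regorafenib If symptomatic, hold Regorafenib until symptoms resolve AND diastolic BP ≤ 90 mm Hg". Without symptoms, regorafenib therefore goes on unchanged.

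The Grade 3 row can be entered in two ways, joined by OR. One is pressure: systolic 160 or above, or diastolic 100 or above. The other is therapy: "More than one drug or more intensive therapy than previously used indicated". The therapy criterion carries no pressure threshold. The dosing instruction is "Hold Regorafenib until diastolic BP ≤ 90 mm Hg, and if symptomatic, until symptoms resolve", so the hold applies with or without symptoms.

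The lead-in in Section 6.3.1.2 leaves the management of hypertension to local standards and the investigator's usual practice, and presents the table's dose reductions as suggestions for use where needed. It adds: "Every effort should be made to control blood pressure by medical means other than study drug dose modification".

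**The concern.** An increase in the dose of a drug the patient already takes is, in plain words, more intensive therapy than before. The Grade 2 branch for treated patients therefore cannot be carried out without also satisfying the Grade 3 therapy criterion. One row then says continue and the other says hold, for the same patient at the same visit.

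What is at stake is consistent dosing across sites. Two investigators can each follow the table faithfully and act in opposite ways.

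Such patients can enter the trial. Section 5.1.2 excludes only hypertension that stays uncontrolled despite optimal management, so patients controlled on medication are eligible. Patients can also join the group on study: one with previously normal pressure who starts a single drug under the Grade 2 row is already treated at the next raised reading.

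**Working it through.** The plan gives no figure to reproduce here. The check applies both rows to a patient already on one antihypertensive drug. The readings are illustrative.

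**Step 1: entry criteria and treatment.** Grade 2 is entered by "Systolic BP 140 - 159 mmHg or diastolic BP 90 - 99 mmHg, OR Symptomatic increase by > 20 mmHg (diastolic) if previously within normal limits". The Grade 3 row lists "Increase current anti-hypertensive medication" among its own treatments. So the table itself associates the same act, raising a current drug, with both grades.

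**Step 2: apply the rows.**

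| Patient on one drug | Grade 2 row | Grade 3 row, via the therapy criterion | Result |
|---|---|---|---|
| 145/95, no symptoms | Raise dose, continue regorafenib | Hold until diastolic is 90 or below; 95 > 90, so the hold takes effect | Direct conflict |
| 145/85, no symptoms | Raise dose, continue regorafenib | Hold until diastolic is 90 or below; 85 ≤ 90, so release is already met | Two rows apply, little or no effect on dosing |
| 145/95, symptoms | Hold until symptoms resolve and diastolic is 90 or below | Hold on the same two conditions | Two rows apply, same immediate action |

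The conflict over dosing is therefore confined to asymptomatic, already-treated patients, mainly those with diastolic pressure above 90 and below 100 and systolic pressure under 160. A patient with previously normal pressure who starts a first drug has a separate Grade 2 instruction and is not part of this point.

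**Step 3: what follows from the row chosen.** For an asymptomatic patient the Grade 2 row has no hold and no dose reduction. The Grade 3 row has both:

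- The hold falls under footnote a, which ends protocol therapy if the delay exceeds 4 weeks.
- If pressure is not controlled by new or stronger therapy, the dose drops one level.
- If Grade 3 recurs despite that, it drops another, and footnote c ends protocol therapy for anyone who would need less than 80 mg daily.

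Section 6.3.1.1 sets the levels at 160, 120 and 80 mg, which are 40 mg apart. From 120 mg, the first reduction gives 120 − 40 = 80 mg and a second gives 80 − 40 = 40 mg, which is below 80, so the patient leaves protocol therapy. From 160 mg, two reductions give 160 − 40 − 40 = 80 mg and the patient stays on.

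**Step 4: look for a tie-break.**

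- Section 6.3.1.1 says to follow the highest grade, but for a subject with more than one toxicity. Here there is one toxicity that meets two rows. If the rule were stretched to cover it, the Grade 2 instruction to step up treatment and continue could never apply to a treated patient.
- Table 6-1 excludes hypertension by its title.
- The lead-in to Table 6-4 leans away from changing study drug but does not say which row governs.

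**The case against.** The best defence is that a sensible site would read the table in sequence: the specific Grade 2 instruction governs the 140-159/90-99 band, and the Grade 3 therapy criterion applies only once that step has failed. On this view the Grade 3 line about raising current medication proves little, because that row must also serve patients at 160 or 100 and above. The reductions are only suggested, and management is left to local practice. This has force and softens the conflict. But the sequence is not written anywhere, and the reading the table does contain leads to a hold.

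The objection also stands against several stronger inferences that a reader might draw:

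- **That reported Grade 3 hypertension incidence will depend on how sites read Table 6-4.** Sections 7.4.1.2, 7.4.1.2.2 and 8.2 grade adverse events by CTCAE, not by this management table. The table's grade column is labelled CTCAE v4.0, but the CTCAE text is not reproduced, so no carry-over into adverse event grading can be shown. Section 8.3 says only "Point estimates and exact binomial (Clopper-Pearson) confidence intervals (CI) will be calculated to estimate the incidence of AEs and SAEs"; it names neither hypertension nor a grade-specific rate. Section 1.3.2 quotes grade 3 or higher hypertension figures of 7% in the colorectal trial and 48.5% in the GIST trial, so there is no settled baseline for a shift in any case.
- **That each hold costs a fixed share of a cycle.** Table 6-4 sets no minimum hold. The 7-day minimum belongs to hand-foot skin reaction in Table 6.3. A hypertension hold ends when its conditions are met, and could be short or overlap the week off drug.
- **That every treated patient in the Grade 2 band is affected.** Step 2 above shows that the effect on dosing is narrower.

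**Conclusion.** The contradiction is real and lies in the table's own wording. It rests on one reading of plain language: that raising the dose of an existing drug counts as more intensive therapy than before. Its practical reach is limited to asymptomatic, already-treated patients, mainly with diastolic pressure above 90 and below 100. Within that group it determines whether study drug is held and whether the later reduction and off-protocol steps can apply.

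The documents give no count of such patients, so no number is put on the frequency or on lost dosing. A reader might infer that the primary result is at risk, but no effect on the PFS6 analysis, the sample size or the decision rule is shown. This is an inconsistency that should be corrected, not a flaw in the design.

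**What to change.** The sponsor's clinical team should reconcile the Grade 2 and Grade 3 rows of Table 6-4 so that an asymptomatic patient already on antihypertensive medication, with pressure in the 140-159/90-99 band, falls under exactly one row with one regorafenib instruction. The lead-in to the table in Section 6.3.1.2 should be brought into line with that choice. No view is offered here on which instruction is right.

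The cost is a wording change in one table and its introductory text, plus a clarification to sites. It adds no visits, procedures or patients, and leaves the statistical analysis as it is.

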6.3.1.1 Dose Reduction and escalation Levels

The starting dose of Regorafenib is 120 mg once daily. The dose will be escalated to 160 mg once daily from the second cycle if no Regorafenib-associated toxicities greater than grade 1 occur during the first cycle.

Study medication will be administered on a 3 weeks on/1 week off schedule [3 weeks out of every 4].

Doses will be delayed or reduced for clinically significant hematologic and non-hematologic toxicities that are related to protocol therapy according to the guidelines shown in the Dose Delays/Dose Modifications table that follows. Dose modifications will follow predefined dose levels. Dose adjustments for hematologic toxicity are based on the blood counts obtained in preparation for the day of treatment.

The modifications of Regorafenib will follow the following predefined dose levels:

Dose level +1	160 mg po qd	Four 40-mg tablets of Regorafenib
Dose level 0 (standard starting dose)	120 mg po qd	Three 40-mg tablets of Regorafenib
Dose level - 1	80 mg po qd	Two 40-mg tablets of Regorafenib

If a subject experiences more than one toxicity, dose reduction should be according to the toxicity with the highest grade

In the case of two or more toxicities of the same grade, the investigator may dose reduce according to that deemed most causally related to study treatment

If a dose reduction has been performed, intra-subject dose re-escalation can be considered (up to the maximal 160 mg daily dose) at the discretion of the treating physician provided that the toxicity(ies) has resolved to baseline.

The following tables outline dose adjustments for toxicities related to study drug except hand-foot skin reaction, hypertension and liver function test abnormalities.

Table 6-1: Recommended dose modification for toxicities except hand-foot-skin reaction, hypertension and ALT/ST/bilirubin

NCI-CTCAE v4.0 ^a	Dose Interruption	Dose Modification ^b	Dose for Subsequent Cycles
Grade 0-2	Treat on time	No change	No change
Grade 3	Delay until ≤ Grade 2 ^c	Reduce by 1 dose level	If toxicity remains < Grade 2, dose re-escalation can be considered at the discretion of the treating investigator. If dose is re-escalated and toxicity (≥ Grade 3) recurs, institute permanent dose reduction.
Grade 4	Delay until ≤ Grade 2 ^c	Reduce by 1 dose level. Permanent discontinuation can be considered at treating investigator's discretion.	

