Grade 2	1 st occurrence	Consider decreasing dose by one dose level and immediately institute supportive measures. If no improvement, interrupt therapy for a minimum of 7 days, until toxicity resolves to Grade 0-1 ^{b, c}
	No improvement within 7 days or 2 nd occurrence	Interrupt therapy until toxicity resolves to Grade 0-1. ^c
	3 rd occurrence	When resuming treatment, treat at reduced dose level ^b
	4 th occurrence	Interrupt therapy until toxicity resolves to Grade 0-1. ^c When resuming treatment, decrease dose by one dose level. ^{b, d} Discontinue therapy
Grade 3	1 st occurrence	Institute supportive measures immediately. Interrupt therapy for a minimum of 7 days until toxicity resolves to Grade 0-1. ^c When resuming treatment, decrease dose by one dose level. ^{b, d}
	2 nd occurrence	Institute supportive measures immediately. Interrupt therapy for a minimum of 7 days until toxicity resolves to Grade 0-1. ^c When resuming treatment, decrease dose by one additional dose level ^{b, d}
	3 rd occurrence	Discontinue treatment permanently.

a. More conservative management is allowed if judged medically appropriate by the investigator.
b. If toxicity returns to Grade 0-1 after dose reduction, dose re-escalation is permitted at the discretion of the investigator if subject has completed one cycle at reduced dose without recurrence of event.
c. If there is no recovery after a 4-week delay, treatment with Regorafenib will be discontinued permanently.
d. Subjects requiring dose reductions below 80 mg daily should go off protocol therapy.
e. The maximum daily dose is 160 mg.

(For studies with combination therapy, consider including the following statement "The other study treatment may be continued").

At first occurrence of HFSR, independent of grade, prompt institution of supportive measures such as topical emollients, low potency steroids, or urea-containing creams should be administered.

Recommended prevention/management strategies for skin toxicities consistent with HFSR are summarized below:

Control of calluses

Before initiating treatment with Regorafenib:

- Check condition of hands and feet.
- Suggest a manicure/pedicure, when indicated.

- Recommend pumice stone use for callus or 'rough spot' removal.

During Regorafenib treatment:

- Avoid pressure points.
- Avoid items that rub, pinch or create friction.

Use of creams

- Non-urea based creams may be applied liberally.

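### Table 6-4 starts the Grade 3 hypertension hold on systolic ≥160 or diastolic ≥100 mm Hg but releases it on diastolic ≤90 alone, so some patients meet hold and release at the same reading

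*Combined protocol and SAP*

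**What the plan says.** Table 6-4 in Section 6.3.1.2 sets the rules for treatment-emergent hypertension. Its Grade 3 row has two kinds of trigger. One is a pressure value, "Systolic BP ≥ 160 mmHg or diastolic BP ≥ 100 mmHg". The other is a need for more than one drug or for more intensive therapy.

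The antihypertensive column gives one numerical goal: "Treat with the aim to achieve diastolic BP ≤ 90 mm Hg". The dosing column says "Hold Regorafenib until diastolic BP ≤ 90 mm Hg, and if symptomatic, until symptoms resolve", and restart is at the same dose level. Two further steps follow. The first is "If BP is not controlled with the addition of new or more intensive therapy, reduce by 1 dose level". The second is another reduction if Grade 3 recurs after a dose reduction. Footnote a takes a patient off protocol therapy after a delay of more than 4 weeks.

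The text above the table leaves antihypertensive management to local standards and usual practice. It asks that pressure be controlled medically before the study drug is modified, and it describes the table's dose reductions as suggestions for use when necessary.

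Table 6-1, which covers most other toxicities, says "Delay until ≤ Grade 2" for Grade 3 events. Hypertension is outside it: "The following tables outline dose adjustments for toxicities related to study drug except hand-foot skin reaction, hypertension and liver function test abnormalities".

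**The concern.** The row that stops the drug looks at both pressures, and the rule that restarts it looks at one. A patient who is Grade 3 only because of systolic pressure can satisfy the release condition and the treatment goal at the moment the hold begins, so the printed hold has no length. A patient who is Grade 3 on mixed readings can be released when diastolic falls to 90, whatever the systolic value is by then.

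What is at stake is patient safety. The protocol names hypertension as a known effect of regorafenib, and restart is at the same dose. The protocol treats systolic pressure as relevant elsewhere: in the exclusion for uncontrolled hypertension (Section 5.1.2) and in the rule on when a patient must contact the site (Section 6.3.1.2). It gives no reason for leaving systolic out of the release.

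**Working it through.** The plan states no figure for this point, so the check is a logical one. S is systolic and D is diastolic pressure, in mm Hg.

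**Inputs (Table 6-4, Grade 3 row)**
- Hold, by pressure: S ≥ 160 or D ≥ 100.
- Release, asymptomatic patient: D ≤ 90.
- Release, symptomatic patient: D ≤ 90 and symptoms resolved.

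**Where hold and release coincide.** D ≥ 100 and D ≤ 90 cannot both be true, so only the systolic trigger can overlap with the release. For an asymptomatic patient the overlap is S ≥ 160 and D ≤ 90.

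| Reading (asymptomatic) | Hold met? | Release met as printed? | Release met if S < 160 is added? |
|---|---|---|---|
| 170/85 | yes | yes | no |
| 160/90 | yes | yes | no |
| 200/88 | yes | yes | no |
| 165/95 | yes | no | no |
| 150/100 | yes | no | no |
| 170/102 | yes | no | no |

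The printed rule works at onset whenever diastolic is above 90. It fails in the first three rows.

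**Later release.** A patient at 165/95 is held at first. If diastolic falls to 90 and systolic does not move, the reading is 165/90. The release is met, although S = 165 is still 165 − 160 = 5 above the value that starts a hold. In the same way, a symptomatic Grade 3 patient can restart with S ≥ 160 once symptoms resolve and D ≤ 90.

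**Margins.** Diastolic must fall by at least 100 − 90 = 10 between trigger and release. No fall is required of systolic. A restart at 170/85 is 170 − 160 = 10 above the systolic trigger, and one at 180/85 is 180 − 160 = 20 above it. No upper systolic bound applies, because Grade 4 is defined by life-threatening consequences and not by a pressure.

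**Comparison with the other dose tables.** Table 6-1 delays a Grade 3 event to Grade 2 or lower. Table 6.3 (hand-foot skin reaction) uses "interrupt therapy for a minimum of 7 days, until toxicity resolves to Grade 0-1" in its Grade 2 row, and its Grade 3 row has the same endpoint. Table 6.5 says "Interrupt dosing, with weekly monitoring until transaminases return to < 3 X ULN or baseline", which is the same measure that triggered the stop. These tables tie the ordinary release to the measure or grade that caused the interruption. Table 6-4 does so for diastolic but not for systolic.

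**With the fix.** If release requires D ≤ 90 and S < 160, any S ≥ 160 fails it and so does any D ≥ 100. No reading then meets both the pressure trigger and the release.

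**How many patients.** Section 1.3.2 prints rates of grade 3 or higher hypertension of 7% (colorectal trial) and 48.5% (GIST trial). Assuming those rates applied to 35 patients gives 0.07 × 35 = 2.45 to 0.485 × 35 = 16.98, or about 2 to 17 patients with Grade 3 or higher hypertension of any pattern. Both trials dosed at 160 mg, whereas this one starts at 120 mg. The share with systolic ≥160 and diastolic ≤90 is not given, so the number affected cannot be derived.

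**The case against.** The strongest reply is that a careful investigator would not restart at 170/85 and that the protocol leaves room not to.

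- Section 6.3.1.2 puts management under local standards, prefers medical control to dose changes, and calls the table's dose reductions suggested. Section 5.2.1 allows withdrawal when continuing would be harmful. This stands as mitigation. It gives no systolic value for restart, and the advisory wording is attached to dose reductions, not to the hold and its release.
- Section 5.1.2 excludes patients whose pressure stays above 140 systolic or 90 diastolic despite optimal management. Read with that definition, a patient still at 170/85 after added therapy is not controlled and is due a dose reduction. This is a reasonable reading and weakens the point. But the definition is an eligibility criterion, Table 6-4 does not refer to it, and the step it would inform lowers the dose without extending the hold.
- The Grade 3 row still applies to a reading of 170/85 at restart. A reader might infer that the protocol plainly authorises dosing at that pressure. It does not: the row contradicts itself there, and a safe reading is available.
- Pressure is checked weekly for the first 6 weeks, so an early problem would be seen soon. From cycle 5, however, the Section 7.1 schedule shows only Day 1 of each 28-day cycle, with extra checks at discretion.

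A reader might also infer that Table 6-4 is the only dose table under which a patient still at Grade 3 can go back on drug. The documents do not support that. Footnote c to Table 6-1 allows treatment to continue after 4 weeks without recovery if the patient is deriving clinical benefit. The comparison with the other tables therefore concerns their ordinary release rule only.

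**Conclusion.** The point holds as a gap in a stated rule. In the Grade 3 row of Table 6-4, the release and the treatment aim omit the systolic pressure that can trigger the hold. For an asymptomatic patient with systolic ≥160 and diastolic ≤90 the printed hold has zero length, and other Grade 3 patients may restart at the same dose with systolic still ≥160. No other section supplies a systolic release value.

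It is a minor patient-safety correction. The conclusion rests on a literal reading of the row and on the two pressure triggers. It makes no claim about frequency. The treatment-intensity trigger lies outside it, and so does the symptomatic Grade 2 hold, since the table continues drug in asymptomatic patients at systolic 140–159. A reader might take an error in a dosing rule as a threat to the efficacy conclusion. Nothing here supports that: PFS6, the 32 evaluable patients and the 79.6% power do not depend on this rule.

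**What to change.** Amend the Grade 3 row of Table 6-4. For holds triggered by a pressure value, hold until diastolic is ≤90 and systolic is <160 mm Hg, and if symptomatic until symptoms resolve. The clinical team may choose a lower systolic value. Below 160 with diastolic ≤90 is Grade 2 or lower, the release grade that Table 6-1 already uses. Add a systolic component to the antihypertensive aim in the same row.

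Do not define controlled pressure as systolic <160. Under that definition 155/85 would count as controlled for the reduction and re-escalation steps, although it exceeds the 140 limit in Section 5.1.2, and the reduction step could be loosened. If the term is defined, use the protocol's own limits: systolic ≤140 and diastolic ≤90.

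The cost is one wording change in an amendment. No new measurement is needed, because both pressures are already recorded. The downside is slightly longer holds for a few patients, with a small chance of reaching the 4-week limit in footnote a. A release at <160 keeps that chance smaller than a stricter value would.
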